9.5.2.12.2 Columbia–Suicide Severity Rating Scale

The Columbia–Suicide Severity Rating Scale (C-SSRS) is an instrument that reports the severity of both suicidal ideation and behavior. Suicidal ideation is classified on a 5-item scale: 1 (wish to be dead), 2 (nonspecific active suicidal thoughts), 3 (active suicidal ideation with any methods [not plan] without intent to act), 4 (active suicidal ideation with some intent to act, without specific plan), and 5 (active suicidal ideation with specific plan and intent). The C-SSRS also captures information about the intensity of ideation, specifically the frequency, duration, controllability, deterrents, and reasons for the most severe types of ideation. Suicidal behavior is classified on a 5-item scale: 0 (no suicidal behavior), 1 (preparatory acts or behavior), 2 (aborted attempt), 3 (interrupted attempt), and 4 (actual attempt). More than 1 classification can be selected provided they represent separate episodes. For actual attempts only, the actual or potential lethality is classified for the initial, most lethal, and most recent attempts.

The paper version of the C-SSRS will be completed at all study visits. At Screening (Visit 1) the C-SSRS will be completed for the patient's lifetime history of suicidal ideation and behavior for *de novo* patients only; for rollover patients, patient's lifetime history of suicidal ideation and behavior data will be copied from Visit 1 in Study VLZ-MD-22 and kept with patients' source documents for this study. At all other visits, the C-SSRS will be completed for ideation and behavior since the previous visit ([Appendix VIII](#)). The C-SSRS will be evaluated and signed at each visit by a qualified staff member (ie, the Investigator or designee that has extensive professional training and experience in assessing mental illness) before the patient leaves the study center.

The patient should not be released from the study center until the results of the C-SSRS are reviewed and the patient is not considered to be at risk. If there is doubt about whether a patient is at risk, the Investigator must obtain appropriate psychiatric consultation. The results of the C-SSRS will be recorded in the eCRF. A copy of the C-SSRS is provided in [Appendix VII](#).

9.5.3 Investigational Product Concentration Measurements

Not applicable.

[figure not shown]
9.5.4 Health Economic and Outcomes Research Assessments

[figure not shown]
[figure not shown]
Not applicable.

[figure not shown]
9.5.5 **Schedule of Assessments**

The schedule of study procedures and assessments is tabulated by visit in the Schedule of Evaluations in Section 2.0. The descriptions of the procedures to be performed at each visit are provided below. Study procedures are for the patient only, unless otherwise specified.

[figure not shown]
9.5.5.1 *Screening (Visit 1)*

[figure not shown]

**9.5.5.2*****Baseline (Visit 2)***

[figure not shown]
**9.5.5.3**

[figure not shown]
End of Weeks 2 and 3 (Visits 3 and 4)

[figure not shown]
9.5.5.4 *End of Week 4 (Visit 5)*

9.5.5.5 End of Week 6 (Visit 6)

[figure not shown]
At Visit 6, the following procedures will be performed:

[figure not shown]
Allergan, plc

[figure not shown]
9.5.5.6 *End of Week 8 (Visit 7)*

At Visit 7, the following procedures will be performed:

[figure not shown]

9.5.5.7 *End of Week 10 (Visit 8)*

[figure not shown]
9.5.5.8 *End of Week 12 (Visit 9)*

[figure not shown]
9.5.5.9

[figure not shown]
End of Week 14 (Visit 10)

9.5.5.10

[figure not shown]
End of Week 16 (Visit 11)

[figure not shown]
9.5.5.11 *End of Week 18 (Visit 12)*

At Visit 12, the following procedures will be performed:

[figure not shown]
9.5.5.12 End of Week 20 (Visit 13)

At Visit 13, the following procedures will be performed:

[figure not shown]

[figure not shown]
Allergan, plc

9.5.5.13 *End of Week 22 (Visit 14)*

[figure not shown]

9.5.5.14 *End of Week 24 (Visit 15)*

[figure not shown]
9.5.5.15

Final or Early Termination Visit, End of Week 26 (Visit 16)

- Schedule next visit:
 - Week 27 (Visit 17) (1 week [\pm 3 days] relative to Week 26 (Visit 16)

9.5.5.16 *Down-taper, End of Week 27 (Safety Follow-up Visit/Visit 17)*

All enrolled patients must complete a Safety Follow-up Visit (Week 27 [Visit 17]).

Any clinical findings obtained during the final assessment, including clinically significant laboratory abnormalities, will be followed until the condition returns to prestudy status, resolves or stabilizes, or can be explained as being unrelated to the investigational product. If a follow-up visit is necessary, it should take place within 30 days of investigational product termination.

9.5.5.17 *Unscheduled Visits*

Unscheduled visits may be conducted by the Investigator as necessary for any safety reason. Assessments to be conducted at these visits will be at the discretion of the Investigator.

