9.1.3 Down-taper Period

[figure not shown]
All patients who complete the 26-week treatment period and patients who prematurely discontinue before completing 26 weeks of treatment will be eligible to enter the 1-week down-taper period.

If the Investigator determines that it is not clinically appropriate for a patient to enter the down-taper period, investigational product may be discontinued, and the patient should be managed in a clinically appropriate manner.

All enrolled patients must complete the Safety Follow-up Visit (Visit 17/Week 27). Additional follow-up visits may be scheduled within 30 days if necessary for safety reasons.

Study Design

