9.2 DISCUSSION OF STUDY DESIGN

This multicenter, flexible-dose study with a 26-week open-label treatment is designed to evaluate the long-term safety and tolerability of flexible doses of vilazodone (15 and 30 mg/day) in pediatric patients with MDD. An open-label study design with no control group was chosen to meet this objective.

The flexible-dose design was selected to examine the relative safety and tolerability of a range of doses of vilazodone based on the Investigator's judgment (ie, in a manner applicable to the expected clinical use). Also, this study was designed with reference to the FDA Guidance for Industry E11 Clinical Investigation of Medicinal Products in the Pediatric Population.

In this pediatric study, Investigators will enroll pediatric patients ages 7 through 17 who met the *Diagnostic and Statistical Manual of Mental Disorders*, Fourth Edition, Text Revision (DSM-IV-TR) criteria for MDD. The MDD diagnosis will be confirmed using the Kiddie Schedule for Affective Disorders and Schizophrenia—Present and Lifetime ([K-SADS-PL]; [Kaufman et al, 1997](#)), a reliable and valid semi-structured interview designed to assess current and past episodes of psychopathology in children and adolescents, covering a broad spectrum of psychiatric diagnoses through separate interviews with the patient and the caregiver. The Children's Depression Rating Scale-Revised (CDRS-R) (Section 9.5.1.2.1) will assess the MDD symptoms and severity.

[REDACTED] The 1-week down-taper has been included to allow a gradual reduction in the concentration of the investigational product to reduce the likelihood of emergence of discontinuation symptoms.

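### As visible, the Visit 17 window lets the last scheduled AE query and last required C-SSRS fall on about day 4 of a one-week down-taper, possibly before the last dose

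*Protocol*

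**What the plan says.** Protocol 9.1.3 states that completers and patients who discontinue early "will be eligible to enter the 1-week down-taper period". Protocol 9.2 gives the purpose of the taper: "to reduce the likelihood of emergence of discontinuation symptoms".

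The headings of Protocol 9.4.5.2 and 9.5.5.16 both associate the down-taper with Visit 17 at the end of Week 27. Section 9.5.5.16 also calls it the safety follow-up visit. Its timing is in 9.5.5.15: one week after Visit 16, plus or minus "3 days] relative to Week 26 (Visit 16".

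Visit 17 is mandatory: "All enrolled patients must complete the Safety Follow-up Visit (Visit 17/Week 27". Anything later is conditional: "Additional follow-up visits may be scheduled within 30 days if necessary for safety reasons". Unscheduled visits (9.5.5.17) are at the investigator's discretion.

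On suicidality, Protocol 9.5.2.12.2 says: "The paper version of the C-SSRS will be completed at all study visits". After screening, each C-SSRS covers the time since the previous visit. Visit 17 is therefore the last required one.

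On AEs, Protocol 9.5.2.1 continues collection to 30 days after the final protocol-defined visit. Under 9.5.2.5, patients are asked about AEs at each visit. In the 30 days afterwards they are reminded to report events themselves, and an event enters the eCRF only if it is serious or judged potentially related to the product.

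The down-taper is analysed as its own period for AEs and for the C-SSRS (Protocol 9.7.6, 9.7.6.1 and 9.7.6.5.1; SAP 11.0, 11.1 and 11.5.1).

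**The concern.** A tolerance of 3 days is ordinary at an interim visit, because the next AE query and the next C-SSRS look back over whatever an early visit left uncovered. Visit 17 has no scheduled successor. The time between an early Visit 17 and the end of a full one-week taper would have no scheduled AE query and no required C-SSRS.

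Safety and tolerability are the study's only objective. The protocol's introduction describes a suicidality signal with antidepressants in youth, and Protocol 9.10 sets up a Data Monitoring Committee to look at suicidal ideation and behaviour. If the last C-SSRS can precede the last dose, the down-taper suicidality table covers a stretch of the taper whose length depends on when the site booked the visit.

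For AEs, the newly emergent AE (NEAE) definition in Protocol 9.7.6.1 and SAP 11.1 carries no causality condition. The post-study eCRF rule in 9.5.2.5 does carry one for non-serious events. After an early visit, that narrower rule could apply while the patient is still taking taper doses.

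**Working it through.** This is calendar arithmetic. The study is descriptive, so no sample-size or power calculation applies.

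**Inputs**
- Taper length: 1 week, taken as 7 days (Protocol 9.1 and 9.1.3).
- Visit 17: 7 days after Visit 16, tolerance 3 days either way (Protocol 9.5.5.15).
- AE collection: to 30 days after the final visit (Protocol 9.5.2.1).
- Assumption: the last taper dose is on day 7 after Visit 16. The taper schedule is not visible, so days 6 to 8 are also shown.

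**The plan's own figures**
- Duration: 1 + 26 + 1 = 28 weeks, as stated in Protocol 9.1.
- Visits: screening and baseline (2), the 14 treatment visits listed in SAP 4.0, and Visit 17 give 2 + 14 + 1 = 17, as stated in Protocol 9.1.

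**Visit 17 window**
- Earliest: 7 − 3 = day 4. Latest: 7 + 3 = day 10.

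**Position relative to a full taper**

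| Visit 17 on day | Taper days left (7 − day) | Share of taper covered | Days from last dose to visit, if last dose is on day 6 / 7 / 8 |
|---|---|---|---|
| 4 | 3 | 4/7 = 57% | −2 / −3 / −4 |
| 5 | 2 | 5/7 = 71% | −1 / −2 / −3 |
| 6 | 1 | 6/7 = 86% | 0 / −1 / −2 |
| 7 | 0 | 100% | 1 / 0 / −1 |
| 10 | 0 | 100% | 4 / 3 / 2 |

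A negative number means that the visit precedes the last dose. At the earliest compliant date, 3/7 = 43% of a full taper follows the visit. If instead the visit itself ends dosing, no dose follows it, but the taper lasts about 4 days rather than the stated 7.

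**AE collection after a day-7 last dose** (visit day + 30 − 7)
- Visit on day 4: 4 + 30 − 7 = 27 days.
- Visit on day 7: 7 + 30 − 7 = 30 days.
- Visit on day 10: 10 + 30 − 7 = 33 days.

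AE collection therefore continues for about 27 to 33 days after the last dose. What stops at Visit 17 is the scheduled query and the required C-SSRS.

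**The case against.** The strongest objection is that the text that would settle the matter is withheld. The taper regimen, the schedule of evaluations and most of the Visit 17 procedures are not shown. SAP Table 16.1-2, which by its title gives the down-taper visit windows, is listed but not shown. Any of these could anchor the visit to the last dose, or could end dosing at Visit 17. This stands, and it limits confidence. It does not remove the point: if the visit ends dosing, an early visit cuts the taper below its stated week, so the visible passages still need reconciling.

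A reader might infer three stronger things that the documents do not support.

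- **That the window and the end-of-taper label contradict each other outright.** They diverge only on the early side. If the taper is defined as running from Visit 16 to Visit 17, no dose follows the visit, and one week is a nominal length.
- **That discontinuation effects are missed and down-taper counts are biased low.** AE collection continues for 30 days after the visit. A withdrawal symptom judged possibly related still reaches the eCRF. TEAE and NEAE counting, and the on-therapy SAE definition, extend to 30 days after the last dose. Section 9.5.5.16 places any necessary follow-up visit within 30 days of stopping the product. Any extra C-SSRS counts towards the most severe ideation and behaviour (SAP 16.4). Possible under-capture is as far as the text goes.
- **That 43% of the taper goes unobserved.** This is the extreme edge of the window under a day-7 last dose. The share of patients seen early is not given, and patients who do not taper are unaffected.

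It is also fair to say that measuring drug-free withdrawal is not a stated aim. The near-zero drug-free time at an on-time visit is therefore not in itself a departure from the plan.

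**Conclusion.** The point holds in a limited form. On the visible text, a compliant Visit 17 can fall on about day 4 of a one-week taper. Then either up to 3 taper days (2 to 4 if the last dose is on day 6 to 8) follow the last scheduled AE query and the last required C-SSRS, or the taper is shorter than stated.

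The exposed data are the down-taper C-SSRS, which has no required later assessment, and non-serious AEs, which depend on patient report and on a relatedness judgement to reach the eCRF. Serious AEs remain collectable for the 30 days after the visit. The amount of under-capture cannot be estimated from the documents.

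This is a cheap improvement to safety capture and does not threaten the study's conclusions. Confidence is low to medium, because it rests on the visible window line and an assumed day-7 last dose.

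**What to change.** Reconcile the Visit 17 assessment window in Protocol 9.5.5.15 and 9.5.5.16 with the taper length, so that for patients who taper the last scheduled AE query and C-SSRS do not precede the last dose. Make the same change in SAP Table 16.1-2 if it does not already do this. One way is to remove the minus side of the window. Check that against the taper schedule: if the last dose falls on day 8, a day-7 visit would still be one day early (7 − 8 = −1).

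Keep the Visit 16/early termination anchor for patients who do not taper, and leave the taper regimen unchanged. If the text not visible here already ties the visit to the last dose, the sponsor need only confirm this and align the line in 9.5.5.15. If Visit 17 is meant to end dosing, the stated one-week length and the window should be reconciled by the sponsor.

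The cost is a line in the protocol and, if needed, one in the SAP, with slightly less scheduling flexibility for sites. No visit or procedure is added. The change does not create drug-free observation time and is not meant to.

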9.6 DATA QUALITY ASSURANCE**9.6.1 Data Monitoring****9.6.2 Data Recording and Documentation**

Data collection will involve the use of the Forest EDC system, to which only authorized personnel will have access.

All data collected in the context of this study will be stored and evaluated per regulatory requirements and applicable guidance for electronic records. Also, data will be stored and evaluated in such a way as to guarantee patient confidentiality in accordance with the legal stipulations applying to confidentiality of data. Study records [REDACTED] will be retained at the site, along with adequate source documentation, according to FDA and ICH requirements. All study records must be available for inspection by FRI, its authorized representatives, and the FDA or other health authorities.

9.7 STATISTICAL METHODS AND DETERMINATION OF SAMPLE SIZE

9.7.1 Patient Populations

Four populations will be considered in the statistical analysis of the study, as specified below.

9.7.1.1 *Screened Population*

The Screened Population will consist of all patients who signed informed consent for this study.

9.7.1.2 *Enrolled Population*

The Enrolled Population will consist of all patients in the Screened Population who were dispensed investigational product.

9.7.1.3 *Safety Population*

The Safety Population will consist of all patients who took at least 1 dose of open-label investigational product

9.7.1.4 *Intent-to-Treat Population*

The Intent-to-Treat (ITT) Population will consist of all patients in the Safety Population who had a baseline and at least 1 postbaseline assessment of the CDRS-R total score.

9.7.2 Patient Disposition

The number of patients in the Screened Population will be summarized overall by study center. The number of patients in the Enrolled, Safety, and ITT populations will be summarized by study center.

[figure not shown]
Screen failures (ie, patients who were screened but not included in the Enrolled Population) and the associated reasons for failure will be tabulated. The number and percentage of patients who complete the open-label treatment period and of patients who prematurely discontinue during the same period will be presented. The reasons for premature discontinuation from the open-label treatment period as recorded on the termination pages of the eCRF will be summarized (number and percentage) for the Safety Population.

All summaries in this section will be presented by patient cohort (rollover patients from Study VLZ-MD-22 and *de novo* patients) and overall.

9.7.3 Demographics and Other Baseline Characteristics

Demographic parameters (eg, age, race, ethnicity, sex, weight, height, body mass index) and other baseline characteristics will be summarized for the Safety and ITT populations. Descriptive statistics (n, mean, SD, minimum, median, and maximum) will be presented for continuous variables, and frequency distributions (counts and percentages) will be presented for categorical variables. Summaries of demographic parameters will be presented by patient cohort (rollover patients from Study VLZ-MD-22, *de novo* patients) and overall.

9.7.3.1 Prior and Concomitant Medication

9.7.4 Extent of Exposure and Treatment Compliance

All summaries in this section will be presented by patient cohort (rollover patients from Study VLZ-MD-22 and *de novo* patients) and overall.

9.7.4.1 *Extent of Exposure*

[REDACTED]

9.7.4.2 *Measurement of Treatment Compliance*

[REDACTED]

9.7.5 *Efficacy Analyses*

For patients who completed the lead-in study (VLZ-MD-22), the baseline for efficacy from the lead-in study will be used as the baseline for this study. For *de novo* patients, the latest nonmissing evaluation of efficacy variables before the first dose of open-label investigational product will be used as baseline.

The efficacy parameters will include the following at selected postbaseline visits:

- Change from baseline in CDRS-R total score
- Change from baseline in CGI-S score
- CGI-I score

Summaries of efficacy parameters will be presented by patient cohort (rollover patients from Study VLZ-MD-22 and *de novo* patients) and overall. Descriptive statistics will be provided by visit for efficacy parameters for the ITT Population during the open-label treatment period, using both last-observation-carried forward and observed-cases approaches. The last-observation-carried forward approach will be used to impute missing postbaseline values.

9.7.5.1 Primary Efficacy Parameter

No efficacy assessments are considered primary in this open-label safety study.

9.7.6 Safety Analyses

The safety analysis will be performed for the open-label treatment period and down-taper period separately using the Safety Population. The safety analyses will be presented by patient cohort (rollover patients from Study VLZ-MD-22 and *de novo* patients) and overall.

The safety parameters will include AEs, clinical laboratory parameters, vital sign measurements, ECG parameters, C-SSRS evaluations, and the change from baseline in the age- and gender-adjusted height (evaluation of growth). For patients who completed the lead-in study (VLZ-MD-22), the baseline for safety from the lead-in study will be used as the baseline for this study. For *de novo* patients, the latest nonmissing evaluation of safety variables before the first dose of open-label investigational product will be used as baseline.

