9.7.6.1 Adverse Events

For patients who completed the lead-in study (VLZ-MD-22), an AE (classified by preferred term) that occurs during the open-label treatment period or during the down-taper period will be considered a treatment-emergent adverse event (TEAE) if it was not present before the date of the first dose of double-blind investigational product in the lead-in study or if it was present before the date of the first dose of double-blind investigational product in the lead-in study and increased in severity during the open-label treatment period or during the down-taper period. If more than 1 AE is reported before the date of the first dose of double-blind investigational product in the lead-in study and coded to the same preferred term, the AE with the greatest severity will be used as the benchmark for comparison with the AEs occurring during the treatment period or during the down-taper period that were also coded to that preferred term. An AE that occurs more than 30 days after the date of the last dose of investigational product will not be counted as a TEAE.

For *de novo* patients, an AE (classified by preferred term) that occurs during the open-label treatment period or during the down-taper period will be considered a TEAE if the AE was not present before the date of the first dose of open-label investigational product or if it was present before the date of the first dose of open-label investigational product and increased in severity during the open-label treatment period or during the down-taper period,. If more than 1 AE is reported before the date of the first dose of open-label investigational product and coded to the same preferred term, the AE with the greatest severity will be used as the benchmark for comparison with the AEs occurring during the open-label treatment period or during the down-taper period that were also coded to that preferred term. An AE that occurs more than 30 days after the date of the last dose of investigational product will not be counted as a TEAE.

An AE occurring during the down-taper period will be considered a newly emergent adverse event (NEAE) if it was not present before the start of the down-taper period or was present before the start of the down-taper period but increased in severity during the down-taper period. An AE that occurs more than 30 days after the date of the last dose of investigational product will not be counted as a NEAE.

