9.7.6.3 Vital Signs

Descriptive statistics for vital signs (ie, sitting radial pulse rate, sitting systolic and diastolic BP, body weight, and height) and changes from baseline values at each visit and at end of study will be presented. In addition, height and weight z scores will be calculated based on growth charts (see Section 9.7.6.5.2).

Vital sign values will be PCS if they meet both the observed-value criteria and the change-from-baseline value criteria. The criteria for PCS vital sign values will be detailed in the Statistical Analysis Plan. The percentages will be calculated relative to the number of patients with baseline values and at least 1 postbaseline assessment. The numerator will be the total number of patients with available baseline values and at least 1 PCS postbaseline value. A supportive listing of patients with PCS postbaseline values will be provided, including the PID number, study center number, and baseline and postbaseline values. A listing of all AEs that occur in patients who have PCS vital sign values will also be provided.

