11.3 VITAL SIGNS

[figure not shown]
Descriptive statistics for vital signs (ie, sitting radial pulse rate, sitting systolic and diastolic blood pressure (BP), body weight, and height) and changes from baseline values at each visit and at the end of the open-label treatment period will be presented. In addition, height and weight z scores will be calculated based on growth charts.

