16.4 REPEATED OR UNSCHEDULED ASSESSMENTS OF SAFETY PARAMETERS

For roll-over patients, the corresponding baseline of the double-blind lead-in study will be used. If a de novo patient has repeated assessments before the date of the first dose of open-label investigational product, the results from the final nonmissing assessment made before the date of the first dose of open-label investigational product will be used as baseline. If the end-of-open-label-treatment period assessments are repeated or if unscheduled visits occur, the last nonmissing postbaseline assessment during the open-label treatment period will be used as the end-of-open-label-treatment-period assessment for generating summary statistics. Likewise, if the end of open-label down-taper period assessments are repeated or if unscheduled visits occur, the last non-missing assessment during the open-label down-taper period will be used as the end-of-open-label-down-taper-period assessment for generating summary statistics. However, all postbaseline assessments will be used to determine PCS values for laboratory parameters, vital signs and ECG parameters, and to determine most severe suicidal ideation and most severe suicidal behavior from C-SSRS. All assessments will be presented in the data listings.

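### Down-taper summaries of vital signs, laboratory tests and ECG have no reference at the start of the taper, so any change from baseline there is mostly on-treatment change

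*Protocol*

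**What the plan says.** **Separate periods.** Protocol 9.7.6 says: "The safety analysis will be performed for the open-label treatment period and down-taper period separately using the Safety Population". SAP 11.0 says the same.

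**One baseline for measured parameters.** Protocol 9.7.6 sets the de novo rule as "the latest nonmissing evaluation of safety variables before the first dose of open-label investigational product will be used as baseline". Rollover patients instead carry a value over from the earlier trial, since "the baseline for safety from the lead-in study will be used as the baseline for this study". SAP 11.0 and 16.4 agree. No readable section gives another reference for the taper.

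**A taper value is derived.** SAP 16.4 says "the last non-missing assessment during the open-label down-taper period will be used as the end-of-open-label-down-taper-period assessment for generating summary statistics". It also says that all postbaseline assessments feed the PCS determinations.

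**PCS rules.** Protocol 9.7.6.3 says "Vital sign values will be PCS if they meet both the observed-value criteria and the change-from-baseline value criteria". For laboratory tests and ECG (9.7.6.2, 9.7.6.4), the percentages are taken among patients who were not PCS at baseline.

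**Adverse events are re-anchored.** Under protocol 9.7.6.1, an event in the taper is newly emergent (NEAE) "if it was not present before the start of the down-taper period", or if it worsened during the taper. SAP 11.1 has the same rule.

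**Vital-sign time points.** Protocol 9.7.6.3 says "changes from baseline values at each visit and at end of study will be presented". SAP 11.3 says "changes from baseline values at each visit and at the end of the open-label treatment period will be presented".

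**The concern.** Analysing the taper separately is useful if its tables show what happened in the taper. The plan secures this for adverse events by restarting the reference when the taper begins. It does not visibly do so for measured parameters, so a reader of a down-taper table of changes from baseline would see mainly what had accumulated before the taper.

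Two misreadings become possible. A shift that developed on drug and did not move in the taper would appear as a down-taper change. A shift that reversed when the drug was withdrawn would appear as no change. A patient who became PCS on treatment and was still PCS a week later would also be counted in the down-taper PCS table, with nothing to separate that patient from one who became PCS during the taper.

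A smaller matter is the term *end of study* in protocol 9.7.6.3. It is not defined there, and it could mean the last on-treatment visit or the visit after the taper.

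**Working it through.** **Inputs**
- Screening about 1 week, open-label treatment 26 weeks, down-taper 1 week; 17 visits; about 28 weeks in all (protocol 9.1).
- Fourteen open-label visits, Weeks 2 to 26 (SAP 4.0).
- Visit 17 is 1 week ± 3 days after Visit 16 (protocol 9.5.5.15).
- Completers and early discontinuers may both enter the taper (protocol 9.1.3).
- L is the number of weeks from the lead-in baseline to the first open-label dose. The documents do not give it; I assume 6 to 12.

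**Reproducing the plan's figures**
- Duration: 1 + 26 + 1 = 28 weeks.
- Visits: 2 (screening, baseline) + 14 + 1 (Visit 17) = 17.

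**Share of the baseline-to-taper-end interval that precedes the taper**
- De novo, t weeks on treatment: t / (t + 1).
  - Completer: 26/27 = 96.3%. Over the visit window, in days: 182/192 = 94.8% to 182/186 = 97.8%.
  - Stops at Week 4: 4/5 = 80%.
  - Stops at Week 2: 2/3 = 66.7%.
- Rollover completer: (26 + L) / (27 + L).
  - L = 6: 32/33 = 97.0%.
  - L = 12: 38/39 = 97.4%.

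These are shares of calendar time. They are not estimates of how much of a particular parameter's change occurs in each period.

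**What the planned change shows.** Let a parameter shift by d on drug and let a fraction r of that shift reverse in the taper.
- Change from pre-treatment baseline at the end of the taper: d(1 − r).
- Change from the last on-treatment value: −rd.
- No reversal (r = 0): the first gives d, the second 0.
- Full reversal (r = 1): the first gives 0, the second −d.

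**Raw height as an illustration**, assuming growth of 4 to 7 cm a year:
- Over 27 weeks: 4 × 27/52 = 2.1 cm to 7 × 27/52 = 3.6 cm.
- Over 1 week: 4/52 = 0.08 cm to 7/52 = 0.13 cm.

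This applies to raw values only. The age- and sex-adjusted z scores (protocol 9.7.6.5.2, SAP 11.5.2) allow for expected growth.

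**PCS counts.** Take a patient who is not PCS at the pre-treatment baseline, PCS at Week 26 and still PCS at Week 27. The Week 27 value meets the criteria against the pre-treatment baseline, and SAP 16.4 uses every postbaseline assessment. If the tables are split by period as 9.7.6 directs, this patient is counted in both.

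**The case against.** Much of the relevant text cannot be seen. Both schedules and the Visit 17 procedures are redacted. SAP 11.2 to 11.4 are only partly readable. The table of down-taper visit windows is listed in SAP 2.1 but not shown. Which parameters are measured at Visit 17 is therefore unknown, and hidden text could contain a taper reference. SAP 16.4 is a general rule for choosing among repeated values and does not itself prescribe a change from pre-treatment baseline. All of this stands. The point must be confined to the readable text and to whatever is measured in the taper.

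The pre-treatment reference also answers a fair question: has the patient returned to the state before the drug? That stands too, and it is why the reference should be kept.

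A reader might infer several stronger claims that the documents do not support:
- **That the whole down-taper safety analysis misses withdrawal.** NEAEs are judged from the start of the taper. After screening, the C-SSRS is rated since the previous visit (protocol 9.5.2.12.2) and reported separately for the taper (SAP 11.5.1). The taper's stated purpose concerns discontinuation symptoms (protocol 9.2), which the NEAE analysis addresses.
- **That a reversal would be hidden.** Vital-sign values and changes are summarised by visit and all assessments are listed, so a reader can compare Week 26 with Week 27. The difference in mean changes equals the mean within-patient change only when the same patients contribute to both, and it does not sort the PCS counts.
- **That every taper change spans at least 26 weeks.** This is false for early discontinuers.
- **That the protocol and SAP conflict on the vital-sign endpoint.** Protocol 9.7.6.3 does not say that the end of study is Visit 17. Sections 9.3.3 and 9.5.5.15 treat Visit 16 as the final assessment, which agrees with SAP 11.3, while 9.1.3 requires all enrolled patients to complete Visit 17. The term is ambiguous; a contradiction is not shown.

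**Conclusion.** The point holds in a limited form. In the readable text, vital signs, laboratory tests and ECG have only a pre-treatment baseline, while the taper is to be analysed separately and adverse events are re-anchored at its start. For any such parameter measured in the taper, most of the interval behind a change from baseline precedes the taper: 96.3% for a de novo completer, about 97% for a rollover completer if L is 6 to 12 weeks, and less for early discontinuers. PCS values that arose on treatment and persist would be counted again.

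This rests on two assumptions: that at least some of these parameters are measured at Visit 17, and that no redacted text supplies a taper reference. The practical effect is small. The synopsis rules out inferential analysis, the objective is long-term safety and tolerability, and no aim to estimate a withdrawal effect on these parameters is stated. It is a worthwhile clarification and does not threaten the study's conclusions.

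**What to change.** 1. In SAP 11.0 and 16.4, keep the pre-treatment baseline. For each vital sign, laboratory or ECG parameter measured in the taper, add the change from the last nonmissing open-label value (Visit 16/ET). This parallels the NEAE reference.
2. Split down-taper PCS values into those newly emergent since that value and those persisting from treatment. Do not count only the new ones, because that would drop unresolved abnormalities from the down-taper table.
3. In protocol 9.7.6.3, define the end-of-study time point so that it agrees with SAP 11.3, the end of the open-label treatment period.

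No new data are needed. The cost is one extra derived reference, and a column or footnote in the down-taper tables to say which reference each figure uses.
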